## **6.6.6 Motor Measures** (UPDRS, Grooved Pegboard, Walking-Balance & GaitRite)

Individuals with Parkinson disease will receive additional motor measures before and after NIR intervention. These include the *Unified Parkinson Disease Rating Scale* for rating disease severity, a task of manual fine motor speed and dexterity (*Grooved Pegboard Task*) and walking speed and balance that is measured using a Gait Rite mat which has digital sensors that records speed and foot placement and other motor measures.

## **6.7 Near-infrared (NIR) Stimulation Protocol**

**Overview:** Participants in both the real and sham conditions will participate in a total of six intervention sessions, 3 sessions a week, over a two-week period. Each session will include 40

minutes of “stimulation” time, followed by completion of a brief adverse events questionnaire and a brief mood questionnaire (POMS). Total session time in the lab may take up to 1.5 hours. During each session, the participant will be seated comfortably in a chair. Clusters of LED’s will be positioned across various regions of the scalp via a flexible head cap. Onset of the NIR light stimulation will be controlled by a MedX Console unit. During the 40 minutes of NIR stimulation or sham stimulation, the participants will view nature documentaries (BBC Life documentary series; Gunton, 2009) that are presented during the period of stimulation. This is being done in order to standardize cognitive engagement and control for differences in cognitive activity during stimulation.

In addition to stimulation in the laboratory, participants may be asked to do daily intranasal stimulation in their home. They will be provided Vielight intranasal devices (described below) and asked to stimulate themselves for 25 minute sessions on the days they do not come to the lab (i.e., 2 days during week 1 and 2 days during week 2).

[figure not shown]
### 6.7.1 Equipment: MedX Rehab Console System.

Near infrared (NIR) stimulation will be delivered to the cranium via two MedX 1116 Rehab Console Systems (MedX Health, LLC, Mississauga, ON, Canada). See Figure 2.

The MedX system was FDA-cleared in 2003 as a Class II medical device (K032231, 21 CFR 890.5500) and has been freely available on the market since that time. It is not viewed as causing harm or injury, and falls under the category of an infrared lamp with indicated use for “increase in local blood circulation” as well as muscle relaxation and relief of muscle and joint aches, pains, and stiffness. It has been used in transcranial studies of cognition and mood in humans since 2009, without any known adverse side effects (See review by Rojas & Gonzalez-Lima, 2013).

Each MedX console consists of a control unit and 3 superluminous diodes - a cluster of LED’s (3 MedX MCT502). Each superluminous LED cluster consists of 52 near infrared diodes and 9 visible red diodes (see Figure 2). The energy delivered by the device is 1 Joule/cm^2 in 45 seconds at treatment wavelength of 870 nm. The LED cluster has an irradiance of 22.2 mW/cm^2 and treats an area of 22.48 cm^2.

In 2013, we were awarded monies from a shared instrumentation grant from the McKnight Brain Institute for purchase of two MedX console systems (each approximately \$5000). Since then we have acquired additional units, including two units that are ‘sham’.

[figure not shown]
Vielight 810 Infrared Light will be delivered intranasally using a Vielight 810 Infrared system (Vielight, Inc., Toronto, ON, Canada). The Vielight 810 Infrared System uses light that is considered safe and painless, and does not require FDA clearance (considered a low-risk device). The Vielight 810 consists of an infrared diode that delivers light at a wavelength of 810 nm, with an irradiance of 7.6 mW/cm^2 and a pulse frequency of 10 Hz.

### 6.7.3 Stimulation Session Procedure

In Lab Sessions: All participants will attend six NIR stimulation sessions. During each session, the participant will be seated comfortably in a chair. Clusters of LED's will be positioned across various regions of the scalp via a flexible nylon head cap that is appropriate to the participants head size. Onset of the NIR light stimulation will be controlled by the MEDX Console. Twenty minutes of stimulation will occur during each Set, for a total of 40 minutes NIR light application, with LEDs repositioned to a new position for each set. During the session, the 810 nm intranasal Vielight will be placed in each nostril and turned on once per session for 25 minutes (one dose) and subsequently removed.

During the actual stimulation period, participants will view nature documentaries (BBC Life documentary series; Gunton, 2009) that are shown on a monitor during the duration of stimulation. This is being done in order to standardize cognitive engagement and control for differences in cognitive activity during stimulation. This will also be done to reduce conversation between the examiners and the participant during the period of stimulation, which could differ between participants. Six episodes of the BBC Documentary will be presented in the same order for each participant, with a different episode played at each stimulation session. A brief description of each episode is provided below:

1. "Challenges of Life": This episode is the series opener and features stories of animal behavior such as feeding, hunting, and courting from around the world. Animals featured include killer whales, poison-dart frogs, and penguins.
2. "Mammals": This episode features the life of mammals from around the globe. Stories feature animals such as reindeer, polar bears, African elephants, and humpback whales.
3. "Birds": This episode features stories of birds from across the globe. Nesting, parenting, and migratory behaviors are described from animals such as humming birds, pelicans, grouses, and bowerbirds.
4. "Creatures of the Deep": This episode features an exploration of life in the deep ocean. Deep-sea creatures such as jellyfish, spider crabs, sea urchins, octopus, and coral reefs are described.
5. "Plants": This episode utilized time-lapse photography and videography to explore the behavior of plants. Featured plants include Venus flytraps, sundews, milkweeds, dragons blood trees and mangrove trees.
6. "Primates": This episode features stories of primates and the attributes that have made them a highly successful group of mammals. Animals featured include lemurs, gibbons, orangutans, and macaques.

Other episodes include "Reptiles and Amphibians", "Fish", "Insects", and "Hunters and Hunted". These videos may be played if there is reason to need an extra video.

At Home Intranasal Sessions (optional). Each participant will be loaned an intranasal device, that is identical to the one used during the laboratory session. Participants will be asked to use the intranasal device for 25 minutes each day, except for days they visit the laboratory. The participants are trained to use the device during the initial lab visit and shown that the device

automatically cuts off after 25 minutes. Participants will be asked to keep a log of usage and to return the device at the completion of the study.

#### Equipment Sterilization

Following each session, the 6 MedX LED clusters and 2 Vielight intranasal leads will be sterilized with disinfectant wipes (PDI Super Sani-Cloth Germicidal Disposable Wipes) before storage. The manufacturer's recommendations are to clean equipment with sterilizing swabs in between sessions. In addition, a new flexible net caps will be used for each participant.

**Questionnaires:** Following the 40-minute stimulation period all participants will fill out the POMS short form and will be queried for adverse events (using the Adverse Events log). Completion of these questionnaires will take place at the end of each session.

#### 6.7.4 SHAM NIR Condition and Blinding

Participants in the sham control group will undergo identical procedures as the intervention group - screening, baseline testing, and LED cluster placement procedures. We have sham devices that look similar in all respects to the active devices, both transcranial and infranasal. The sham and active devices are coded and only one of the Investigators knows the code. The research assistant administering the stimulation sessions will not be aware of the participant's treatment status, and will have no role in post-intervention assessments. The research assistant administering post-intervention testing will be blinded to the treatment status of the participant.

#### 6.8. Optional Research MRI: Exploratory Aim

A subset of participants, from the Real and Sham Intervention groups will participate in collection of neuroimaging data, obtained before and after the intervention. This is an exploratory aim and designed to obtain pilot data. This portion of the study will be coordinated by [name], an expert in multimodal imaging with older adults. We plan to obtain:

- structural MRI
- resting state fMRI. This will allow us to examine intervention changes in functional connectivity.
- Blood flow. This will allow us to examine changes in brain perfusion
- spectroscopy data using a newly acquired MRI/S head coil. The latter will allow us to assess for region-specific changes in phosphorous MRS-based markers of ATP function, one of the presumed mechanisms of NIR stimulation.

After giving informed consent and undergoing the appropriate prescreening measures, eligible participants will receive pre-intervention and post-intervention brain scans at the McKnight Brain Institute on the AMRIS 3T Philips scanner utilizing a dual tuned 31P-1H MRS coil.

Structural MRI scans are also acquired as part of this scanning protocol. Inside the brain scanner, participants will lie on a padded table with foam pads used to hold the participants head in place. During this portion of the study, participants will be asked to lie as still as possible. There will be no specific task or behavior that the participant must engage in. We anticipate that this protocol will take 1 hour. Specifics are shown below.

**Neuroimaging Methods.** We will conduct neuroimaging on a 3.0 Tesla Philips research dedicated scanners with a research agreement supporting all scanner sequences. We will use a Rapid MR International dual tuned 31P-1H MRI/S head coil for data acquisition.

**MRI protocol.** The scanning sequences will take 1.5 hour to acquire: 1) Structural MRI (MPRAGE), 2) Phosphorous MR Spectroscopy (31P-MRS) and 3) fMRI (EPI-BOLD).

**Structural MRI.** Whole brain axial gradient-echo MPRAGE T1-weighted images will be acquired for 31P and fMRI localization (TE/TR 3.57/2730ms, flip angle = 7 degrees, slice thickness=1mm, Gap=0 (contiguous slices), FOV=25.6cm, 256×256 matrix size & 2.0×2.0mm resolution; 5 minutes duration). 2D/3D FLAIR imaging will be acquired, time allowing within the 1.5 hour scan, to assess white matter hyper-intensity load (~6 minutes duration). High resolution hippocampal imaging will be performed, time allowing within the 1.5 hour scan, to allow localization of functional connectivity analysis seeds in the hippocampus and frontal regions and assessment of possible structural improvements related to intervention (~5 minutes duration). 3D PASL sequence (TE/TR=10.5/4885ms, PLDelay=2000ms, 1.9x1.9x4mm resolution, FOV = 240 x 240 x 160mm) will enable quantification of changes in cerebral perfusion related to intervention. Data will be analyzed using AFNI to compute regional and whole brain estimates of resting cerebral perfusion pre and post intervention.

**Phosphorous MRS.** A 31P-MRS pulse-acquired sequence will be acquired from two 6-cm^3 voxels centered in prefrontal cortex and temporal cortex to assess region-specific change in phosphorous MRS-based markers of ATP function and brain health. Parameters: TE 0.1ms; TR 4500ms; Spectral resolution 2.4 Hz/point; Spectral bandwidth 3000 Hz; 7 minutes duration). Analyses: Spectra will be analyzed using Tarquin to give concentrations for the following phosphorous metabolites: nucleoside di- and tri-phosphate (gamma, alpha, beta-NTP), phosphoethanolamine (PEtn), phosphocholine (PCho), glycerophosphoethanolamine (GPEtn), glycerophosphocholine (GPCho), 2,3 diphospho-glyceride (DPG), inorganic-phosphate (Pi), membrane-bound phospholipid (MP), and phosphocreatine (PCr). The signal amplitudes of brain tissue and CSF will be derived (corrected for T2 decay), with brain water signal used to correct for partial CSF volume. MRS Quality Assurance: The concentration measures for the metabolites will be accepted with Cramer-Rao lower bounds (%SD) of less than 20%, a reliable estimate for a particular metabolite for group comparisons. Scans resulting in spectra that do not meet quality criteria will be repeated. Line width and signal-to-noise resonance ratios are plotted over time (brain, phantom) to monitor spectral quality; inter- and intra-subject variability assessed by correlation and Bland and Altman plots.

**fMRI.** We will perform an fMRI resting state block using echoplanar BOLD imaging (EPI) methods, with a TR of 2500ms, TE 16ms, field of view = 192mm, matrix = 64 and voxel size of 3.5mm^3. fMRI processing and analyses will use Statistical Parametric Mapping 12 (SPM12). We will present one ten minute block of resting state fMRI before and after intervention to provide insight into stimulation related change in functional networks. We will construct time series datasets implementing preprocessing methods to minimize physiological and motion artifact, with each volume assigned a condition based on task sequence. Whole-brain voxel-wise multiple regression analysis will verify activation patterns in resting state networks. Appropriate covariates, such as movement, for each participant's brain voxels will be included using the variation in BOLD signal over time. The REST toolbox and local specialized software will be used to obtain total interdependence (TI) values to assess functional connectivity between nodes in the resting state network, with particular focus on change in hippocampal connectivity. Primary dependent measures

will TI between each resting state ROI's per participant (FWE threshold  $p<.05$ ). TI values will compare intervention-related changes in functional connectivity.

Shown below is an overview of the temporal overview of the procedures.

Table 2: Overview of Procedures and Protocol

Measures	Pre-sceen	Screening	Base-line	Pre-MRI*	Intervention	Follow-up	Post-MRI*
Telephone Screening	X	X					
Inclusion / Exclusion		X					
Informed Consent		X					
Demographic Info		X					
Medical History		X					
MoCA or DRS-2		X					
HVLT-R or WMS-III LM		X				X	
Mental Health Screen V.3		X					
Charleson		X					
Medications		X					
WTAR or WRAT-IV		X					
Vision Screen		X					
Digit Span (WIT)		X					
TrailMaking Test			X			X	
Wisconsin Card Sort			x			x	
Digit Symbol (WIT)			X			X	
Category Fluency		X					
JLO		X					
Functional Activity Questionnaire (FAQ)			X				
Cognitive Function Inventory (CFI)			X			x	
Cognitive Function Inventory –Study Partner (not PD)			X				
Clinical Dementia Rating Scale -Study Partner (MCI group only)			X				
Demographic Info - Study Partner (Not PD)			X				
MRI Screener**		X*		X*			X*
Cognitive Change Index (CCI)			X			X	

Skintype Questionnaire			X			
Arena Task			X			X
AVTL			X			X
MST			X			X
NIH Examiner			X			X
Stroop			X			X
CalCap (processing speed)			X			X
UPDRS (PD only)			X			X
Grooved Pegboard (PD only)			X			X
Walking-Balance (PD only)			X			X
BDI-II			X			X
STAI			X			X
Apathy Scale			X			X
NIH Toolbox Emotion			X			X
POMS			X		X	X
Fatigue Severity Scale			X			X
Pittsburgh Sleep Quality Index			X			X
Pain Rating Scale			X			X
Adverse Events Log					X	X
Expectation Quest		X				
Placebo Control Quest						X

\*MRI, only a subset of participants will be asked to undergo pre and post-MRI; these will be screened for eligibility using a standard MRI screener\*\*. MoCA=Montreal Cognitive Assessment; HVLT-R=Hopkins Verbal Learning Test – Revised; WMS-III LM = Wechsler Memory Scale, Logical Memory subtest; Charlson = Charleson Comorbidity Index; WTAR=Wechsler Test of Adult Reading; JLO = Judgement of Line Orientation; Skin type Questionnaire =Fitzpatrick Skin-Type Questionnaire; AVT=Auditory Verbal Learning Test; MST = Mneumonic Similarity Test; CalCap = California Computerized Assessment Package; UPDRS = Unified Parkinson Disease Rating Scale; BDI-II=Beck Depression Inventory, 2nd edition; STAI=State Trait Anxiety Inventory; POMS=Profile of Mood States, Short Form; PCQ=Placebo Control Questionnaire; ; Daily journal = completed by participant for recording time of daily intranasal treatment.

- Note that individuals with Parkinson disease will receive the Unified Parkinson Disease Rating Scale, Grooved Pegboard Test, and Gait Rite analysis before and after intervention. Other participants will not.

## 7 Outcome and Statistical Approaches

### 7.1. Outcome Measures

Aim 1 examines executive function and memory using sensitive cognitive measures.

- Co-Primary Executive Outcome: Changes in pre-post treatment scores on: a) executive composite and domain scores derived from the NIH Examiner and b) the Stroop interference score.

- Co-Primary Memory Outcomes: Changes in pre-post treatment scores on memory measures including a) delayed recall scores and composite from the Arena and b) delayed recall score from the AVLT. Secondary outcomes include other executive and memory measures as well as potential mediator and moderator variables such as processing speed.

Aim 2 examines well-being and mood variables.

- Co-Primary outcome: Changes in pre-post treatment scores on the Negative Affect and Psychological Wellbeing scales from the NIH Toolbox emotion module.
- Secondary outcomes: Changes in pre-post treatment scores on traditional mood measures including the 1) State-Trait Anxiety Inventory (STAI; Spielberg, 1989), the 2) Profile of Mood States (POMS; Curan et al., 1995), 3) Beck Depression Inventory-II (BDI-II; Beck et al., 1996), and 4) Apathy Scale.

Aim 3 is an exploratory neuroimaging aim that will examine changes in resting state functional connectivity as a function of group status (NIR stimulation vs Control). We are particularly interested in potential changes in MRS spectroscopy, particularly those elements associated with phosphorous ATP

Aim 4 pertains to motor variables that are being examined in patients with Parkinson disease

- Outcomes include: Changes in pre-post intervention scores on the Grooved Pegboard Task, scores on the UPDRS rating scale, and gait and balance measures on the GAIT-Rite scale.

## 7.2. Randomization and Statistical Methods

**7.2.a. Randomization.** Participants in the Cognitively Normal, the MCI, and Parkinson groups will be independently assigned to Sham and Treatment groups on a 1:1 ratio. For the Cognitively Normal group, we anticipate an N of 35 in each treatment group. For each MCI group, we anticipate an N of 10 per treatment group. For the PD group, we anticipate an N of 20 per treatment group. Randomization will be stratified according to age and MoCA/MMSE scores so as to prevent different average ages or cognitive status scores between the treatment groups. Treatment assignment will be pseudorandomized in order to have comparable distributions of age and cognitive screening scores across Sham and Treatment interventions. Procedures will be followed so that group assignments are not available to individuals administering and scoring baseline/pre-intervention and post-intervention cognitive/mood data.

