### **6.4 Inclusion/Exclusion criteria**

#### **6.4a. General Inclusion Criteria for all Participants**

- Age 62 years or above
- Able to provide informed consent and perform cognitive and mood measures on a computer
- Willingness to be randomized to Sham or Real intervention
- Can devote 2 weeks to the intervention, and additional time for pre and post testing
- 8th grade education and ability to read on 8th grade level based on scores on the Wechsler Test of Adult Reading (WTAR) or the Wide Range Achievement Test-IV (WRAT-IV); or a reading test at 14 pt. text
- On stable doses of major medications; Since some older adults with memory complaints may be prescribed acetylcholinesterase inhibitors or related medications by their primary care physicians (i.e., donepezil, rivastigmine, galantamine, memantine, or other potential memory-enhancing agent(s), we will not exclude them as long as they have been on stable medications for at least two months and plan to continue this medication during study participation.

- Willingness to allow a study partner (spouse, family member, friend) to answer questions about their cognitive, mood, and other behaviors. This does not apply to individuals with Parkinson disease.

6.4b. General Exclusion Criteria for All Participants

- Sensory loss (vision, hearing) or motor deficits that would preclude participation in the experimental cognitive tasks or neuropsychological assessment
- Unstable and uncontrolled medical conditions (metabolic encephalopathy, HIV, moderate to severe kidney or liver disease)
- Previous major strokes or other known significant brain abnormalities or diseases affecting cognition (i.e., multiple sclerosis, seizure disorder, brain surgery, moderate TBI, etc.). No history of brain surgery. Exceptions are a diagnosis of Parkinson's disease for the PD subgroup.
- Evidence of potential dementia based on cognitive screening (e.g., scores < 5th %ile on the Montreal Cognitive Assessment (MoCA) or the Dementia Rating Scale-2 (DRS-2) based on appropriate age, education and sex norms.

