### **Parkinson Disease Group**

- Participants must have a diagnosis of idiopathic Parkinsons disease by a movement disorders specialist based on UK Brain Bank criteria (Hughes et al., 1992a, 1992b).
- No previous history of brain surgery (DBS, pallidotomy, thalamotomy, or fetal cell implants).
- No evidence of dementia based on scores on a cognitive screener (e.g., Dementia Rating Scale-2 (DRS-2) and score on delayed paragraph recall cannot be lower than 1.0 standard deviation of normative values
- May have difficulties with activities of daily living, but this is due to physical symptoms of Parkinson disease and not because of cognitive problems
- Unwillingness to undergo baseline and followup visits when they are 'off' standard dopamine medication
- Inability to undergo a brain scan

Additional exclusion criteria apply to those individuals who participate in the ***optional brain imaging*** study. The brain scan is optional for all participants except those with Parkinson disease. In that case, inability to undergo a brain scan, before and after intervention, is an exclusion. Exclusion criteria for a brain scan include

- Presence of claustrophobia
- Implants such as pacemakers, heart valves, brain aneurysm clips, orthodontics, non-removable body jewelry, or shrapnel containing ferromagnetic metal.

\*\*Note that we are highly experienced in working with older adults who are identified as experiencing current major depression or other psychological disturbances or who perform below cutoff on standard cognitive screening measures. The PI [[name]] is a boarded clinical neuropsychologist who has been working with this clinical population for over 30 years. The clinical Co-Is ([name], [name], [name], [name]) are experienced neurology clinicians, and the doctoral students on this protocol are clinical psychologists in training with experience in diagnosis and treatment of mood and cognitive disorders. Discussions will be held with individuals of concern and recommendations will be made to appropriate health care providers with permission of the participant and in line with standards of care.

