### **6.5 Screening Interview and Measures**

Participants will be screened for inclusion/exclusion criteria. This will involve review of background and demographic information, medical and psychiatric history, current medications, and assessment of functional activities, along with screening of current cognitive

status using the MoCA or DRS-2, the HVLT-R or WMS-III Logical Memory, and other cognitive measures. Screening will be administered by the project coordinator.

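### The cognitive stratifier names the MMSE, which is never given, and omits the permitted DRS-2, so it is undefined for anyone screened only on the DRS-2

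*Protocol*

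**What the plan says.** Section 7.2.a says that the cognitively normal, MCI and Parkinson participants "will be independently assigned to Sham and Treatment groups on a 1:1 ratio". It then states: "Randomization will be stratified according to age and MoCA/MMSE scores". The next sentence adds: "Treatment assignment will be pseudorandomized in order to have comparable distributions of age and cognitive screening scores". That second sentence names no instrument.

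The screening sections describe a different pair of tests. Section 6.5 lists "MoCA or DRS-2, the HVLT-R or WMS-III Logical Memory". The dementia exclusion in section 6.4b refers to scores on the "Montreal Cognitive Assessment (MoCA) or the Dementia Rating Scale-2 (DRS-2) based on appropriate age, education and sex norms", with a cut-off at the 5th percentile. Table 1 and the schedule in Table 2 also give the MoCA or the DRS. For the Parkinson cohort the criterion reads "No evidence of dementia based on scores on a cognitive screener (e.g., Dementia Rating Scale-2 (DRS-2", and the MoCA is not mentioned there.

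Section 7.3 analyses each cohort separately with a 2 (arm) by 2 (occasion) mixed ANOVA. Age appears only in additional analyses, as a possible predictor of change or a moderator. The cognitive screening score appears in none of the analyses.

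**The concern.** The stratifier is part of the allocation rule, so it has to be a quantity that each participant has when allocated. As written, one of its two cognitive tests is never given and one of the two tests that may be given is not in it. Staff who follow section 7.2.a literally cannot place a participant screened only on the DRS-2 in a cognitive stratum, and would have to improvise.

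Two further points in the same part of the plan compound this. The text says both that randomisation is stratified and that assignment is pseudorandomized to make distributions comparable. These may be one procedure or two, and the reader cannot tell which will be run. In addition, the models in section 7.3 omit the factors that the design balances on, so they do not use the precision that balancing on a prognostic factor can offer.

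What is at stake is modest: a clear, reproducible allocation in small cohorts, and an analysis that matches it.

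**Working it through.** The plan gives no figure to reproduce on this point. The check is a comparison of sections, followed by a range for the share affected.

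**Which cognitive screener is named where**
- Section 7.2.a, first sentence on stratification: MoCA/MMSE.
- Section 7.2.a, next sentence: cognitive screening scores, no test named.
- Section 6.4b, exclusion: MoCA or DRS-2, judged against norms.
- Section 6.4c, Parkinson: DRS-2, given as an example.
- Section 6.5 text: MoCA or DRS-2.
- Table 1: MoCA or DRS.
- Table 2: one row for MoCA or DRS-2 at screening. There is no MMSE row, and the MMSE is not in the abbreviation list.

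The MMSE thus occurs once, in the stratifier. The DRS-2 is allowed in every place that describes screening and is absent from the stratifier. No section maps MoCA and DRS-2 scores to common strata.

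**Is a score available at allocation?** Yes. Section 6.6 randomises participants who have met the study criteria, and meeting them requires the dementia screen. Everyone therefore has a MoCA or a DRS-2 result. The gap lies in how the factor is named and mapped, not in the data.

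**Could the two tests mix within one cohort?** The protocol allows it without stating it. Section 6.5 also lets MCI and Parkinson participants from the clinics reuse screening results up to 2 months old, so the test may depend on the source of recruitment.

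**Share without a MoCA score.** Inputs from section 6.2: 70 cognitively normal, 20 amnestic MCI, 20 nonamnestic MCI and 40 Parkinson. Total = 70 + 20 + 20 + 40 = 150. The assignment of screeners to cohorts is an assumption in each line.
- Everyone gets the MoCA: 0/150 = 0%.
- Only the Parkinson cohort gets the DRS-2: 40/150 = 26.7%.
- Parkinson and both MCI cohorts get it: (40 + 20 + 20)/150 = 80/150 = 53.3%.
- Everyone gets the DRS-2: 150/150 = 100%.

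Only the second line has any pointer in the text, and that pointer is an example, not a rule.

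**Cost of adjusting in the smallest cohort.** An MCI group has 10 + 10 = 20 participants. The arm-by-occasion test then has 20 − 2 = 18 residual degrees of freedom. Two one-parameter covariates leave 18 − 2 = 16.

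**The case against.** The strongest reply is that this is a naming slip with an obvious intent. The sentence after the stratifier asks only for "comparable distributions of age and cognitive screening scores across Sham and Treatment interventions". Each cohort is randomised and analysed on its own, so a Parkinson cohort tested throughout on the DRS-2 could simply be stratified on the DRS-2. The exclusion criterion already reads both tests against norms. The study is also a short pilot, and block sizes or minimisation settings are commonly left to another document.

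Most of this stands, and it limits the point. Several stronger readings are tempting, and the protocol does not support them.
- A reader might infer that many participants lack the stratifier. No section gives the split between screeners, so this is not established.
- A reader might infer that balancing cannot be done. It can, by using one screener within each cohort or normed strata across both.
- A reader might take pseudorandomized to mean that staff choose arms by hand to match groups. Nothing says so. The word fits constrained or computer-generated allocation equally well, and the preceding sentence calls the process stratified randomisation.
- A reader might infer that the stratifier could not serve as a covariate. With separate analyses per cohort, a single screener or a normed score could.
- A reader might measure the harm by chance imbalance at 10 per arm, sqrt(2/10) = 0.45 SD. That describes unstratified allocation in an MCI group. It does not measure the effect of a misnamed factor, and no section ties the MCI groups to the DRS-2 in particular.

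What the reply does not remove is the contradiction itself. A stated aim of comparable scores is not a rule for forming strata, and the one rule that is given leaves out a permitted test.

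**Conclusion.** The point holds as a contradiction within the protocol. The cognitive stratifier in section 7.2.a conflicts with sections 6.4b, 6.4c and 6.5 and with Tables 1 and 2, and it is undefined for anyone screened only on the DRS-2. The share affected is between 0% and 100% of the planned 150. It is 27% under the one assumption that has a textual hint, namely that the Parkinson cohort, and only that cohort, uses the DRS-2.

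The wording on pseudorandomized allocation is ambiguous, not shown to be faulty. The models in section 7.3 leave out the cognitive factor altogether and use age only in supplementary analyses. None of this shows bias in the comparison of arms. It is a defect in an operative rule that is cheap to correct and should be corrected.

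**What to change.** 1. In section 7.2.a, delete the MMSE and reconcile the stratifier with the screening sections in one of two ways. Either name the single screener used in each cohort, or stratify on the age-, education- and sex-normed percentile from section 6.4b for whichever test was given. The second option also covers reused clinic results. Percentiles from two tests are only roughly comparable, which is adequate for forming strata.
2. Replace pseudorandomized with a statement that allocation within each cohort follows one procedure: a stratified random list, or minimisation with a random element.
3. In section 7.3, include age and this screening factor as covariates in the models for the outcomes. In the 2 by 2 layout each needs its interaction with occasion (equivalently, a regression of change on arm, age and the screening factor). A main effect alone leaves the arm-by-occasion test unchanged.

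The cost is protocol wording, a short randomisation script and one or two degrees of freedom, for example 18 down to 16 in an MCI group of 20. No additional data are collected, because every participant already has a screening score.
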